4. Availability of either archival tumor tissue or fresh core or excisional biopsy of a tumor lesion (primary or metastatic, excluding bone biopsies) is mandatory to determine HMGA2 expression level prior to enrollment. Fine needle aspirates are not acceptable. Tumor material must be suitable for biomarker assessment as described in the Laboratory Manual. If an archival sample is submitted during Prescreening for HMGA2 testing, a fresh tumor biopsy during the Screening period is additionally encouraged if feasible for exploratory biomarker analysis.
5. HMGA2 high tumor expression is required. If a tumor specimen is assessed as not evaluable for HMGA2 expression by the central laboratory, another sample may be submitted to assess for HMGA2 high status. The status of tumor HMGA2 expression (high versus not high) will be determined by a centralized RT-PCR assay with predefined cutoff

(documented in the applicable documentation submitted to the Food and Drug Administration [FDA]) and with appropriate regulatory status.

6. Have Eastern Cooperative Oncology Group (ECOG) PS of 0 to 1 at study entry and Day 1 of treatment with bintrafusp alfa.
7. Life expectancy \geq 12 weeks as judged by the Investigator at study start.
8. Have adequate organ function:
 - a. Adequate hematological function defined by absolute neutrophil count $\geq 1.5 \times 10^9/L$, platelet count $\geq 100 \times 10^9/L$, and hemoglobin (Hgb) $\geq 9 \text{ g/dL}$.
 - b. Adequate hepatic function defined by a total bilirubin level \leq the upper limit of normal (ULN), aspartate aminotransferase (AST) and alanine aminotransferase (ALT) levels $\leq 1.5 \times \text{ULN}$. For participants with liver involvement in their tumor, AST $\leq 5.0 \times \text{ULN}$, ALT $\leq 5.0 \times \text{ULN}$, and bilirubin $\leq 3.0 \times \text{ULN}$ are acceptable.
 - c. Adequate renal function defined by creatinine $\leq 1.5 \times \text{ULN}$ or calculated creatinine clearance (CrCL) $\geq 30 \text{ mL/min}$ for participant with creatinine $> 1.5 \times \text{ULN}$ (glomerular filtration rate can also be used).

Note: CrCL should be calculated per institutional standard. If no local guideline is available, CrCL should be calculated using the Cockcroft-Gault Method:

$$\text{CrCL} = ([140-\text{age}] \times \text{weight [kg]} \times [0.85 \text{ for females only}]) / (72 \times \text{creatinine}).$$

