- Isolated laboratory values out of normal range that do not have any clinical correlation. Discuss with Medical Monitor regarding work-up, management, and treatment continuation versus hold versus discontinuation for isolated Grade 4 laboratory abnormalities
- If alternative explanation is identified for Grade 4 non-tumor bleeding.

See [Appendix 5](#) for guidance on specific Grade 4 irAEs, as most require permanent treatment discontinuation.

Grade 3 treatment-related TEAEs

1. Participants with any severe or Grade 3 treatment-related adverse reactions that recur should be permanently discontinued. Exceptions may be considered for the following after discussion with Medical Monitor:

- Transient Grade 3 flu-like symptoms or fever that is controlled with medical management
- Transient Grade 3 fatigue, local reactions, headache, nausea, emesis that resolves to \leq Grade 1 or baseline
- Tumor flare phenomenon defined as local pain, irritation, or rash localized at sites of known or suspected tumors
- Any Grade ≥ 3 drug-related amylase or lipase abnormality that is not associated with symptoms or clinical manifestations of pancreatitis

- Grade 3 Hgb decrease (< 8.0 g/dL) that is clinically manageable with blood transfusions or erythroid growth factor use
- Increases in ECOG PS ≥ 3 that resolves to ≤ 2 by Day 1 of the next infusion (i.e., infusions should not be given if the ECOG PS is ≥ 3 on the day of treatment and should be delayed until ECOG PS ≤ 2)
- KA and cutaneous squamous cell carcinoma (cSCC)
- Grade 3 non-tumor bleeding requiring intervention or hospitalization if alternative explanation can be identified (such as concomitant use of antithrombotic agents, traumatic event, etc).

2. See [Appendix 5](#) for guidance on specific Grade 3 irAEs as many require permanent treatment discontinuation, including pneumonitis and nephritis.
 - AST or ALT > 5 times ULN or total bilirubin > 3 times ULN must be permanently discontinued, except for participants with liver metastases (e.g., who begin treatment with Grade 2 AST or ALT). These participants should be discontinued if AST or ALT increases by $\geq 50\%$ relative to baseline and lasts for at least 1 week.
3. Persistent Grade 3 adverse reactions (excluding endocrinopathies controlled with hormone replacement therapy) that do not recover to Grade 0 to 1 within 12 weeks after last dose of treatment.

Grade 2 treatment-related TEAEs

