Laboratory parameters with NCI-CTC grades not available**Table 13 Non-NCI-CTC Gradable Parameters**

Parameter (LBTEST)	Parameter code
Biochemistry	
Bilirubin direct	BILDIR
Bilirubin Indirect	BILIND
Chloride	CL
C-Reactive Protein	CRP
Total Protein	PROT
Urea	UREA
Urea Nitrogen	UREAN
Hematology	
Absolute Basophils	BASO
Absolute Monocytes	MONO
Absolute Reticulocytes	RETI
Basophils/Leukocytes	BASOLE
Eosinophils/Leukocytes	EOSLE
Erythrocytes (RBC)	RBC
Hematocrit	HCT
Lymphocytes/Leukocytes	LYMLE
Mean Corpuscular Hemoglobin	MCH
Mean Corpuscular HGB Concentration	MCHC
Mean Corpuscular Volume	MCV
Monocytes/Leukocytes	MONOLE
Neutrophils/Leukocytes	NEUTLE
Reticulocytes/Erythrocytes	RETIRBC
Coagulation	
Prothrombin Time/Standard Prothrombin Time*	PTS

* reported on the "Coagulation" eCRF page.

For all non-gradable parameters, the following summaries will be displayed:

- Number and percentage of participants by lowest on-treatment value (classified as normal, high, low)
- Number and percentage of participants by highest on-treatment value (classified as normal, high, low)
- Shift from baseline to highest/lowest on-treatment value (classified as normal, high, low)

Separate listings of hematology (including coagulation) and biochemistry will be created. Each listing will include: participant identifier, age, sex, race, first dose date, last dose date, laboratory parameter (units), visit, date, SI value, change from baseline value, lower limit of normal, ULN,

indicator of normal range (low, normal, high), toxicity grade according to NCI-CTCAE (when applicable) and highest/lowest on treatment value flag. Baseline and post-baseline values after the on-treatment period will be flagged. These listings will be sorted by participant identifier, parameter and laboratory measurement date.

Liver function tests

ALT, AST and total bilirubin are used to assess possible drug induced liver toxicity. The ratios of test result over ULN will be calculated and classified for these three parameters during the on-treatment period.

The number and percentage of participants within each of the following liver function categories during on-treatment period will be described:

- ALT < 3×ULN, ALT ≥ 3×ULN, ALT ≥ 5×ULN, ALT ≥ 10×ULN, ALT ≥ 20×ULN
- AST < 3×ULN, AST ≥ 3×ULN, AST ≥ 5×ULN, AST ≥ 10×ULN, AST ≥ 20×ULN
- (ALT and AST) < 3×ULN, (ALT or AST) ≥ 3×ULN, (ALT or AST) ≥ 5×ULN, (ALT or AST) ≥ 10×ULN, (ALT or AST) ≥ 20×ULN
- Total Bilirubin (TBILI) < 2×ULN, TBILI ≥ 2×ULN

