- Concurrent ALT ≥ 3×ULN and TBILI ≥ 2×ULN
- Concurrent AST ≥ 3×ULN and TBILI ≥ 2×ULN
- Concurrent (ALT or AST) ≥ 3×ULN and TBILI ≥ 2×ULN
- Concurrent (ALT or AST) ≥ 3×ULN and TBILI ≥ 2×ULN and ALP > 2×ULN
- Concurrent (ALT or AST) ≥ 3×ULN and TBILI ≥ 2×ULN and ALP ≤ 2×ULN or missing

Concurrent measurements are those occurring on the same date.

Categories will be cumulative, i.e., a participant with an elevation of AST ≥ 10×ULN will also appear in the categories ≥ 5×ULN and ≥ 3×ULN.

A plot of peak ALT versus peak total bilirubin, both relative to the ULN will be provided. This eDISH plot (evaluation of drug-induced serious hepatotoxicity) will be divided into 4 quadrants by the lines through ALT ≥ 3×ULN and total bilirubin ≥ 2×ULN. The left lower quadrant is then considered normal or insignificant elevations in liver chemistries, the upper quadrants indicate participants with possible Gilbert's cholestasis; the right upper quadrant are the possible Hy's Law participants; the right lower quadrant is possible Temple's Corollary (participants with ALT ≥ 3×ULN but not satisfying Hy's Law). Same plot will be provided for AST.

In addition, a listing of all total bilirubin, ALT, AST and ALP values for participants with a post-baseline total bilirubin ≥ 2×ULN, ALT ≥ 3×ULN or AST ≥ 3×ULN will be provided.

Urinalysis/urinalysis microscopic evaluation, hormonal tests, tuberculosis test and serology

All test results for urinalysis /urinalysis microscopic evaluation, hormonal tests, serum and serology parameters will also be listed in dedicated listings:

- Urinalysis parameters:
 - Urinalysis full parameters: physical appearance, pH, specific gravity, protein, glucose, ketones, nitrite, leukocyte esterase, blood, urobilinogen, bilirubin, color
 - Urinalysis microscopic parameters: erythrocytes (RBC), leukocytes (WBC), epithelial cells, bacteria, crystals, casts
- Tuberculosis parameters: M. tuberculosis IFN Gamma Response by T-SPOT ELISPOT, Tuberculosis skin test (TST), M. tuberculosis IFN Gamma Response by QuantiFERON TB Gold ELISA
- Hormonal parameters: thyroxine free (Free T4), thyrotropin (Thyroid-Stimulating Hormone; TSH)
- Serology parameters: hepatitis B virus (HBV), hepatitis C virus (HCV), hepatitis B DNA, hepatitis C RNA

Pregnancy test

Results for pregnancy and post-menopausal status as collected on the “Pregnancy Test” eCRF page will also be listed:

- Pregnancy parameters (serum or highly sensitive urine human chorionic gonadotropin [hCG])

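### The SAP 15.3 liver categories and eDISH plots ignore baseline, so a participant with liver involvement can count as possible Hy's Law with no on-treatment change

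*SAP*

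**What the plan says.** **SAP 15.3, Liver function tests.** The purpose is stated first: "ALT, AST and total bilirubin are used to assess possible drug induced liver toxicity". The classification is then by ratio to ULN only: "The ratios of test result over ULN will be calculated and classified for these three parameters", within the on-treatment period. The planned table is introduced by "The number and percentage of participants within each of the following liver function categories during on-treatment period will be described". Its rows include "ALT < 3×ULN, ALT ≥ 3×ULN, ALT ≥ 5×ULN, ALT ≥ 10×ULN, ALT ≥ 20×ULN", the same set for AST, "Total Bilirubin (TBILI) < 2×ULN, TBILI ≥ 2×ULN", and concurrent rows that combine ALT or AST of at least 3 × ULN with bilirubin of at least 2 × ULN on the same date, with and without a split by ALP. The eDISH plots show peak ALT (and, separately, peak AST) against peak bilirubin, both as multiples of ULN, with lines at 3 × and 2 × ULN. Of the result the SAP says that "the right upper quadrant are the possible Hy's Law participants". None of these displays has a baseline condition.

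**Protocol 5.1, inclusion criterion 8b.** The general limits are 1.5 × ULN for AST and ALT and 1 × ULN for bilirubin. A relaxed set begins "For participants with liver involvement in their tumor, AST" and goes on to accept AST and ALT up to 5.0 × ULN and bilirubin up to 3.0 × ULN.

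**Where the documents do use baseline.** Protocol 6.8 has an exception worded "except for participants with liver metastases (e.g., who begin treatment with Grade 2 AST or ALT", under which AST and ALT are judged by their rise over baseline. In SAP 15.4, every blood pressure, pulse and respiratory abnormality needs both a threshold and a change from baseline, and the weight criteria are percentage changes.

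**The concern.** The liver displays are meant to screen for drug-induced toxicity, and immune-related hepatitis is listed in protocol 6.9.2 as an important identified risk. A ULN threshold screens well when everyone starts near normal. Here eligibility deliberately admits a group that may start above the threshold, and it is the group whose tumour is the obvious competing explanation. The trial has one arm, so no control group shows how many participants would cross these lines from liver disease alone. The participant's own baseline is the main reference available, and the table and plots do not use it. At stake is how a small safety count reads: with planned enrolment of 29, one point in the possible Hy's Law quadrant draws attention whether or not anything happened on treatment.

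**Working it through.** The documents give no figure for this point to reproduce. The check compares entry limits with display cutoffs.

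**Step 1. Can a value that satisfies criterion 8b already meet the cutoff?**

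| SAP 15.3 category (× ULN) | Liver involvement: AST/ALT ≤ 5.0, bilirubin ≤ 3.0 | No liver involvement: AST/ALT ≤ 1.5, bilirubin ≤ 1.0 |
|---|---|---|
| ALT or AST ≥ 3 | yes | no |
| ALT or AST ≥ 5 | only at exactly 5.0 | no |
| ALT or AST ≥ 10, ≥ 20 | no | no |
| Bilirubin ≥ 2 | yes | no |
| Concurrent ≥ 3 and ≥ 2 | yes | no |
| Right upper eDISH quadrant | yes | no |

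The ALP-split rows behave like the concurrent row, because criterion 8b sets no ALP limit.

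**Step 2. What does one plotted point mean?** Take a point at ALT 4 × ULN and bilirubin 2.5 × ULN.

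- Participant with liver involvement who entered at those values: 4/4 = 1.0 × baseline and 2.5/2.5 = 1.0 × baseline. Nothing changed.
- Participant without liver involvement: baseline was at most 1.5 and 1.0 × ULN, so the rise is at least 4/1.5 = 2.7 × baseline and 2.5/1.0 = 2.5 × baseline.

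More generally, a participant without liver involvement must at least double both tests to reach the quadrant (3/1.5 = 2.0 and 2/1.0 = 2.0). A participant who entered at the relaxed ceilings stays in it even if ALT falls by 40% (1 − 3/5) and bilirubin by 33% (1 − 2/3). The display treats all of them alike.

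**Step 3. How many participants?** The documents give neither the share with liver involvement (f) nor the share of those who enter past both cutoffs (g). Both are assumptions. With n = 29 and independent participants, the expected count is n × f × g and the chance of at least one is 1 − (1 − f × g)^n.

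| f | g | Expected count | Chance of at least one |
|---|---|---|---|
| 0.20 | 0.02 | 29 × 0.004 = 0.12 | 11% |
| 0.30 | 0.10 | 29 × 0.03 = 0.87 | 59% |
| 0.40 | 0.20 | 29 × 0.08 = 2.32 | 91% |

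Each such participant adds 1/29 = 3.4 percentage points. The range is wide because the inputs are unknown; it shows that the effect could be nil or could be the whole count.

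**The case against.** The case for leaving the plan alone has real force.

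- **These are screening displays.** The wording is possible toxicity and possible Hy's Law; no causality is assigned and no decision rule is attached. This stands. A reader might infer that the SAP reports liver disease as drug-induced liver injury, but the text does not say that.
- **Baseline can be recovered elsewhere.** SAP 15.3 also plans shift tables from baseline to worst grade for ALT, AST and bilirubin, change-from-baseline boxplots, a biochemistry listing with change from baseline, and a listing of all bilirubin, ALT, AST and ALP values for anyone crossing a cutoff. So it would be wrong to say that metastatic disease and drug injury cannot be told apart. What remains is that the shift tables treat one test at a time, and no described output marks who met the joint criterion at baseline.
- **Immune-related hepatitis has its own algorithm.** SAP 15.2.3.2 requires onset or worsening after first dose, treatment with agents such as corticosteroids or immunosuppressants, and either no clear other cause (underlying cancer is named as one) or a consistent biopsy. That risk is not identified from these categories. This stands.
- **The protocol rule is a different thing.** Section 6.8 governs stopping treatment, and its baseline-relative part covers AST and ALT, not bilirubin. It shows that baseline was thought relevant; it does not contradict the SAP display. The vital-sign criteria in SAP 15.4 are the closer comparison.
- **Early discontinuation.** SAP 4.1 replaces summary tables with listings as deemed appropriate, so the category table may never be produced. This reduces the practical effect. Section 4.1 does not say whether the eDISH figures are dropped.

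**Conclusion.** The point holds in a limited form. As written, the ≥ 3 × ULN, bilirubin ≥ 2 × ULN and concurrent categories, and the right upper eDISH quadrant, can include participants with liver involvement who did not change on treatment. The ≥ 5 × ULN category is reachable at entry only at the exact limit, the 10 × and 20 × ULN categories not at all, and participants without liver involvement are outside the problem. The effect is confined to this table and these plots.

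Two further inferences are not supported. One is that a true worsening from a normal baseline would be diluted: these are counts of participants and individual points, so one participant's inclusion does not remove another. The other is to apply an assumed 20–30% liver-involvement rate to 29 and read the resulting 6 to 9 participants as false cases. They are only those admitted under the relaxed limits; a false case in the quadrant also needs both tests past their cutoffs at entry. The size is 3.4 percentage points per participant at the planned 29, and 0.1 to 2.3 expected participants under the stated assumptions (20–40% with liver involvement, 2–20% of those past both cutoffs). Actual enrolment was low according to SAP 4.1, so fewer participants are likely and each would weigh more. This is a cheap improvement to a safety display, not a flaw in the trial's conclusions.

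**What to change.** In SAP 15.3, for the liver category output, both eDISH plots and the liver listing:

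1. Mark each participant who already met the cutoff at baseline (baseline as defined in SAP 9.2), separately for ALT, AST and bilirubin and for the joint criterion.
2. Next to each existing count, report the number newly meeting the cutoff on treatment.
3. For participants above ULN at baseline, show the peak as a multiple of baseline beside the multiple of ULN.
4. Show liver-metastasis status as a flag. A full split is not advised: SAP 8.2 defines that subgroup for efficacy endpoints only, and the cells would be too small to read.

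If SAP 4.1 leaves only listings, the marks in the liver listing are enough. The cost is SAP wording, a little programming and a slightly busier display. The data are already planned for collection, and no eligibility, dosing or stopping rule is touched.

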15.4 Vital Signs

All vital sign parameters from the on-treatment period, except oxygen saturation, will be summarized using descriptive statistics (mean, SD, median, Q1, Q3, minimum, and maximum) of actual values and changes from baseline for each visit over time. End of treatment visit will be summarized separately. The changes computed will be the differences from baseline.

The following potentially clinically significant abnormalities will be summarized:

- ≤ 95 mmHg and decrease from baseline ≥ 20 mmHg in systolic blood pressure
- ≥ 140 mmHg and increase from baseline ≥ 20 mmHg in systolic blood pressure
- ≤ 45 mmHg and decrease from baseline ≥ 20 mmHg in diastolic blood pressure
- ≥ 90 mmHg and increase from baseline ≥ 20 mmHg in diastolic blood pressure
- ≤ 50 beats/min and decrease from baseline ≥ 20 beats/min in pulse rate
- ≥ 100 beats/min and increase from baseline ≥ 20 beats/min in pulse rate

- ≤ 20 breaths/min and decrease from baseline ≥ 5 breaths/min in respiratory rate
- ≥ 20 breaths/min and increase from baseline ≥ 5 breaths/min in respiratory rate
- $\geq 10\%$ weight decrease
- $\geq 10\%$ weight increase

A listing of vital signs will be provided including participant identifier, age, sex, race, vital sign parameter, visit, date, time, value, unit and change from baseline. Baseline values and post-baseline values collected after the on-treatment period will be flagged.

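### The low respiratory-rate criterion uses the same limit as the high one (20 breaths/min), so for baselines up to 25 it reduces to any fall of at least 5

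*SAP*

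**What the plan says.** SAP 15.4 introduces a list of thresholds with the words "The following potentially clinically significant abnormalities will be summarized". Two items concern respiratory rate:

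- Low: "≤ 20 breaths/min and decrease from baseline ≥ 5 breaths/min in respiratory rate". The part in question is "20 breaths/min and decrease from baseline", where 20 is the upper bound for a low value.
- High: "≥ 20 breaths/min and increase from baseline ≥ 5 breaths/min in respiratory rate".

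The blood pressure items have the same two-part form, an absolute limit plus a change from baseline, but with different limits in the two directions. Systolic pressure has "≤ 95 mmHg and decrease from baseline ≥ 20 mmHg in systolic blood pressure" and "≥ 140 mmHg and increase from baseline ≥ 20 mmHg in systolic blood pressure". Diastolic pressure has "≤ 45 mmHg and decrease from baseline ≥ 20 mmHg in diastolic blood pressure", with 90 mmHg as the high limit. Pulse uses 50 and 100 beats/min. Weight has a change condition only, 10% either way.

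No other section of the protocol or SAP gives a different respiratory-rate limit or a reason for sharing one. According to the SAP's modification history, version 2.0 edited the listing described in section 15.4; the shared limit stands in the current text.

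**The concern.** In a two-part rule the absolute limit is there to restrict the flag to values that are extreme in themselves, and the change condition to values that are new for that participant. Setting both respiratory-rate limits at 20 removes the first safeguard on the low side. Everything below the SAP's own high threshold then counts as low enough, and only the size of the fall decides.

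At stake is how specific one safety count is. Applied literally, the summary puts participants whose raised rate has come down in the same row as any participant whose rate has become slow, and labels both potentially significant.

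**Working it through.** There is no stated figure to reproduce, so the check is on what the rule does.

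**Inputs (all SAP 15.4).** Let b be the baseline and v the post-baseline value, in whole breaths/min.

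- Low rule: v ≤ 20 and b − v ≥ 5.
- High rule: v ≥ 20 and v − b ≥ 5.

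**Step 1: when does the low limit matter?** The change condition gives v ≤ b − 5. If b ≤ 25, then b − 5 ≤ 20, so v ≤ 20 is already implied and the limit does nothing. It first matters at b = 26, where 26 to 21 is a fall of 5 that is not flagged.

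**Step 2: comparison with the other paired signs.** Any rule of this form has baselines at which the absolute part is redundant. With low limit L, high limit H and required change d, the low limit is redundant for b ≤ L + d.

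| Sign | L | H | H − L | d | Low limit redundant for b up to L + d |
|---|---|---|---|---|---|
| Systolic (mmHg) | 95 | 140 | 45 | 20 | 115 |
| Diastolic (mmHg) | 45 | 90 | 45 | 20 | 65 |
| Pulse (beats/min) | 50 | 100 | 50 | 20 | 70 |
| Respiratory rate (breaths/min) | 20 | 20 | 0 | 5 | 25 |

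For the first three, redundancy ends well below the high limit (115 < 140, 65 < 90, 70 < 100). For respiratory rate it extends past it (25 > 20). A participant who starts in the range the SAP treats as high can therefore be flagged low without the limit ever being tested.

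**Step 3: enumeration.** Take all whole-number pairs with v ≥ 8 and a fall of at least 5.

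- Baselines 12 to 20: 1 + 2 + … + 8 = 36 pairs, of which 36 are flagged.
- Baselines 12 to 24: 1 + 2 + … + 12 = 78 pairs, of which 78 are flagged.
- Baselines 10 to 30: 171 pairs, of which 156 are flagged. The 15 not flagged all have baselines of 26 to 30.

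These are counts of possible pairs, not expected numbers of participants.

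**Step 4: examples.**

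- 20 to 15, 18 to 13 and 24 to 19 are flagged low.
- 22 to 16 is flagged, although the participant has left the range at or above 20.
- 25 to 20 is flagged low, although it ends on the high cut-off.

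**Step 5: would a distinct limit change the result?** As an assumption sweep only, for baselines 12 to 20, low limits of 8, 10, 12 or 14 would flag 8, 21, 30 or 35 of the 36 pairs, against 36 at the limit of 20. The documents do not say which value was meant.

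**The case against.** The strongest reply is that little depends on this. SAP 4.1 says that, after the decision to stop early, listings will be delivered in place of summary tables where appropriate. The vital-signs listing in SAP 15.4 shows values and changes, and flags only baseline values and values after the on-treatment period. It never applies the 20 breaths/min limit. The table may not be produced at all. This stands and sets the size of the point, but SAP 4.1 leaves discretion and the criterion remains in the current text.

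It can also be said that the SAP accepts change-only rules, since weight has one. That is true, but the weight items carry no absolute limit. If a change-only rule had been intended for falls in respiratory rate, no limit would have been needed.

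A reader might also infer more than the documents support:

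- **That ordinary values are flagged as such.** They are not. A fall of at least 5 is always required, and the documents do not define an ordinary respiratory rate.
- **That a value of exactly 20 could be counted in both directions.** It meets both absolute limits, but one measurement cannot be both 5 above and 5 below the same baseline.
- **That every other vital sign has separated limits.** This holds for systolic pressure, diastolic pressure and pulse. Weight is change-only, and body temperature, which protocol 8.2.2 requires, has no criterion in the list.
- **That slow breathing after infusion reactions or opioid use would be hidden.** Protocol 6.5.2 allows narcotic agents for pain, but no passage links either situation to a low rate. The infusion-reaction symptoms named in protocol 6.9.1 include dyspnea and wheezing, not slow breathing. A very low value would still appear in the listing, and in the minimum by visit if tables are run.

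**Conclusion.** The low respiratory-rate criterion is wrong as written. It shares its limit with the high criterion, unlike the other paired absolute limits in the list, and for baselines of 25 or less that limit has no effect. The conclusion rests only on the SAP's own thresholds and arithmetic; no outside norm for respiratory rate is needed.

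The consequence is minor. It concerns the specificity of one descriptive safety count that may not be tabulated. No efficacy endpoint and no treatment decision rule in the documents uses it. How many participants would be flagged depends on their baseline rates and changes, which the documents do not give.

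**What to change.** In SAP 15.4, reconcile the two respiratory-rate items: replace the 20 in the low criterion with a lower limit distinct from the high one, taken from the sponsor's standard. Keep the required fall of at least 5 breaths/min and leave the high criterion as it is. The listing needs no change, because it carries no abnormality flag.

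The cost is one number in the SAP and the matching line in the program, if the summary is run. No data collection, sample size or other analysis is affected.
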